8.2 SERIOUS ADVERSE EVENT (SAE)

A Serious Adverse Event (SAE) includes any of the following events:

- Results in death
- Is life threatening
- Requires subject hospitalization or prolongation of existing hospitalization
- Requires invasive surgical intervention to fix the problem
- Results in persistent or significant disability/incapacity
- Is considered an important medical event

An important medical event that may not meet one of the above definitions might be considered as an SAE if it jeopardizes the health of the subject or requires surgical intervention to prevent one of the outcomes listed in the above definition. Elective hospitalization after the procedure that was planned prior to subject enrollment is not to be considered as an SAE.

8.3 UNANTICIPATED ADVERSE DEVICE EFFECT (UADE)

An Unanticipated Adverse Device Effects (UADE) is any serious adverse effect on health or safety, or any life-threatening problem or death caused by, or associated with, a device, if that effect was not previously identified in nature, severity, or degree of incidence in protocol, subject informed consent form, or application, or any other unanticipated serious problem associated with a device that relates to the rights, safety, or welfare of subjects. Anticipated adverse events are listed as known risks in **Section 12.1**.

8.4 Assessing, Recording and Reporting AEs, SAEs, and UADEs

Only non-serious AEs that are classified by the Investigator as either device-related or procedure-related will be reported. All SAEs, regardless of relationship to the Rotation Medical Rotator Cuff System, and all UADEs will be reported.

An AE may be volunteered spontaneously by the subject or discovered as a result of questioning or physical examination by the Investigator or study staff. The following information should be reported on the Adverse Event CRF as soon as the Investigator becomes aware of the event and updated as needed until event resolves:

- Date of AE onset
- Date the Investigator became aware of the AE
- Main complaints/symptoms of the AE
- Relationship to the study device
- Relationship to the study procedure
- Status of the adverse event

Source documents (e.g., procedural notes, treatment notes, or a signed clinical summary) may be required as supporting documentation for the reported AE.

9 MALFUNCTIONS

Failure of the Rotation Medical Rotator Cuff System to meet its performance specifications or to perform as intended will be documented on the Malfunction CRF. In the event of a malfunction, every effort must be made to return the suspected Rotation Medical device or instrument to the Sponsor for analysis. Malfunctions will be evaluated for reportable requirements through the FDA medical device reporting (MDR) system.

10 PROTOCOL DEVIATIONS

Investigators are required to adhere to the study protocol, signed Clinical Trial Agreement (CTA), applicable national or local laws and regulations, and any conditions required by the appropriate IRB/EC or applicable regulatory authorities.

A protocol deviation is used to describe situations in which the protocol was not followed (this includes all activities at each scheduled visit or activities occurring outside of the

study windows). All attempts should be made to obtain Sponsor approval of the deviation prior to their occurrence.

An Investigator must notify the Sponsor and the reviewing IRB/EC of any deviation from the Study Protocol that was done to protect the life or physical well-being of a subject (medical emergencies). Such notice should be given within 5 days of the occurrence. The Sponsor will determine if the subject affected is to continue in the study.

Documentation of deviations identified by the investigational center, the monitor, or other Sponsor representative(s) will be entered into the Protocol Deviation CRF for the purpose of tracking Investigator compliance with the protocol. The investigational center will be required to document actions taken to prevent recurrence of deviations. The Sponsor representative will initiate corrective actions based on individual deviations or trending reports as appropriate.

11 REPORTING REQUIREMENTS

Table 11-1 shows a summary of all reporting requirements. In addition to this list, individual IRBs may add additional reporting requirements and/or require a different notification time frame.

Type of Report	Prepared by Investigator FOR	Notification Time Frame		
Death ¹	Sponsor & IRB	Within 24 hours of knowledge		
Withdrawal of IRB approval	Sponsor	Within 5 working days of knowledge		
Protocol Deviation to Protect Subject Life or Physical Well-Being	Sponsor & IRB	Within 5 working days of knowledge		
Unanticipated Adverse Device Effect (UADE)	Sponsor & IRB	Within 10 working days of knowledge		
¹ Copies of death records, medical records for the events that led to the subject's death, a death				

Table 11-1: Summary of Reporting Requirements

¹Copies of death records, medical records for the events that led to the subject's death, a death certificate (if available), and an autopsy report (if performed) should be requested.

12 RISKS AND BENEFITS

12.1 RISKS AND RISK MITIGATION

Study patients will be informed of all known potential side effects and complications associated with the study assessments and study procedure prior to enrollment in the study.

There are no known incremental risks to the subject for participating in the study. The risks associated with participating in this study are the same as if the patient is treated outside of the study using the same commercially-available device and include the following potential risks of rotator cuff surgery performed under general or regional anesthesia:

- Tissue inflammation
- The need for repeated surgery because tendons do not heal properly or tear again
- Pain or stiffness that won't go away
- Fever and/or infection
- Complication from anesthesia
- Nerve or blood vessel damage
- Adverse reaction to device

In addition, subjects will be required to undergo MR imaging. MRI is generally a welltolerated procedure and there is no ionizing radiation involved with MR imaging The potential risks are minimal and include claustrophobia, coil element heating and peripheral nerve stimulation, although the latter two are considered highly unlikely, given that the subjects will be imaged within preset safety guidelines to eliminate peripheral nerve stimulation. Coil element heating ranges from a mild sensation of heat to a potential burn. This is considered highly unlikely, as the coils have all undergone extensive testing and clinical use, and special pads are placed surrounding all contact points.

All Investigators will undergo training and subjects will be screened and evaluated for medical histories/conditions that may compromise safe, successful completion of any of the study assessments or performance of the device. Subjects with a known hypersensitivity to bovine-derived materials will not be enrolled in the study.

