7 STUDY ASSESSEMENTS

The schedule of protocol-required study assessments is provided in **Table 7.1**. Adverse event (AE) reporting as required and defined in **Section 8** begins at the time of enrollment (i.e. intra-operative confirmation of eligibility) and concludes at the end of the study.

	Baseline	Procedure	3-Month	1 Year	2 Year
Study Evaluation	Within 60 Days of Surgery	Within 60 Days of Baseline	± 15 days	± 45 days	±90 days
Informed Consent	\checkmark				
Medical History & Exam	\checkmark				
Eligibility Assessment	\checkmark	✓1			
Enrollment (Date of Surgery)		✓			
MRI	\checkmark^2		\checkmark^2	√ ²	\checkmark^2
ASES Survey	√ ³		√ ³	√ ³	√ ³
Constant-Murley Survey	\checkmark		\checkmark	✓	\checkmark
Procedure Data		✓			
Medications	\checkmark^4	✓4	\checkmark^4	\checkmark^4	✓4
Adverse Events		✓ ⁵	√ ⁵	√ ⁵	√5
Recovery/Satisfaction			✓	✓	✓
Questionnaire					
Revision/Additional			√ ⁶	√ ⁶	√ ⁶
Shoulder Surgery					

 Table 7-1: Schedule of Study Assessments

¹Eligibility confirmation will be performed at the time of the study surgery to ensure the rotator cuff tear location/size meets eligibility criteria. Patients whose rotator cuff tears do not meet study eligibility criteria will not be enrolled in the study.

²Each study MRI must be performed in accordance with the MRI study guideline.

³The ASES-Patient Assessment is required. The ASES-Physician Assessment (ROM; strength) is optional as strength and ROM assessments are included in the Constant-Murley survey.

⁴Only prescription medications to treat the index shoulder will be recorded.

⁵Non-serious AEs will only be recorded if they are classified as either possibly or definitely related to either the study device or the study procedure.

⁶Any additional surgical intervention performed on the index shoulder will be reported.

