7.7 FOLLOW-UP ASSESSMENTS

All subjects will undergo post-operative study assessments at 3 months, 1 year, and 2 years after discharge from the study procedure as described below and summarized in **Table 7.1**.

7.7.1 3-Month (± 15 Days) Follow-Up

- 1. Perform an MRI per the Sponsor imaging guidelines.
 - Provide the Sponsor with a de-identified digital copy of, or access to, the MRI.
- 2. Administer the Constant-Murley shoulder survey.
 - Range of motion (ROM) should be measured with a goniometer and strength should be measured with a dynamometer. NOTE: Strength or ROM testing at 3-Month Follow-Up may not be possible due to subject discomfort or ongoing rehabilitation and therefore missed or incomplete strength or ROM testing at this visit will not be considered as a protocol deviation.
- 3. Administer the ASES shoulder survey.
 - Completion of the ASES patient assessment section is required. Completion of the ASES physician assessment section is optional since ROM and strength are assessed during administration of the Constant-Murley survey.
- 4. Administer the recovery/satisfaction questionnaire.
- 5. Record prescription medications.
 - *Record any prescription medications the subject is taking at the time of the follow-up visit to treat his/her index shoulder.*
- 6. Record any new adverse events and update the status of any ongoing, previouslyreported adverse events.
- 7. Report any new revision/additional shoulder surgeries performed on the index shoulder.

7.7.2 1-Year (± 45 Days) Follow-Up

- 1. Perform an MRI per the Sponsor imaging guidelines.
- Provide the Sponsor with a de-identified digital copy of, or access to, the MRI.
- 2. Administer the Constant-Murley shoulder survey.
 - *Range of motion (ROM) should be measured with a goniometer and strength should be measured with a dynamometer.*
- 3. Administer the ASES shoulder survey.
 - Completion of the ASES patient assessment section is required. Completion of the ASES physician assessment section is optional since ROM and strength are assessed during administration of the Constant-Murley survey.
- 4. Administer the recovery/satisfaction questionnaire.
- 5. Record prescription medications.

- *Record any prescription medications the subject is taking at the time of the follow-up visit to treat his/her index shoulder.*
- 6. Record any new adverse events and update the status of any ongoing, previouslyreported adverse events.

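### Section 12.1 denies any added risk of participation yet lists the risks of study-required MRIs, and the adverse event rule gives non-serious harms from those MRIs no clear recording category

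*Combined protocol and SAP*

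**What the plan says.** **Risk statement.** Section 12.1 says "There are no known incremental risks to the subject for participating in the study", and continues: "The risks associated with participating in this study are the same as if the patient is treated outside of the study", using the same commercial device. It lists the risks of rotator cuff surgery and then turns to imaging: "In addition, subjects will be required to undergo MR imaging". On the size of those risks it says "The potential risks are minimal and include claustrophobia, coil element heating and peripheral nerve stimulation", describes the last two as highly unlikely, and adds "Coil element heating ranges from a mild sensation of heat to a potential burn".

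**MRI schedule.** Section 7.7 says "All subjects will undergo post-operative study assessments at 3 months, 1 year, and 2 years after discharge from the study procedure", and MRI is the first item at each of the three visits. Table 7-1 shows the same three scans plus one at baseline.

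**Adverse event rule.** Section 8.4 says "Only non-serious AEs that are classified by the Investigator as either device-related or procedure-related will be reported". Footnote 5 to Table 7-1 says that non-serious events "will only be recorded if they are classified as either possibly or definitely related to either the study device or the study procedure". Item 3 of Section 4.4.1 applies the same two categories to the safety outcome. The relatedness items that Section 8.4 lists for the Adverse Event CRF are the study device and the study procedure, with no others.

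**Serious events.** Sections 4.4.1 and 8.4 report every SAE whatever its cause.

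**The concern.** There are two linked problems.

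First, Section 12.1 makes a flat statement and then contradicts it. If the protocol obliges a subject to be scanned, and scanning carries named risks, those risks belong to participation unless the scans would have happened anyway. The protocol does not say that they would.

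Second, the safety data are filtered by two relatedness categories, the device and the procedure. A minor skin burn or an episode of claustrophobia caused by a follow-up scan comes from neither the implant nor the operation. An investigator who attributes it correctly has no obvious box for it, and the rule then tells the site not to report it. What is at stake is the consistency of the risk statement and the capture of minor harms from the one physical risk that Section 12.1 itself sets out on top of the surgical treatment.

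**Working it through.** The plan gives no figure to reproduce here. The check is a comparison of text plus one count.

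**Step 1: do the sentences in Section 12.1 conflict?**

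| Statement in Section 12.1 | Implication |
|---|---|
| "There are no known incremental risks to the subject for participating in the study" | Added known risk: none |
| "In addition, subjects will be required to undergo MR imaging" | MRI is a requirement, presented as an addition |
| "Coil element heating ranges from a mild sensation of heat to a potential burn" | Added known risk: not none, though rated small |

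The statements could all be true only if the follow-up scans were routine care. No section says so. Section 7.8 also mentions protocol-required visits and routine post-operative visits as separate kinds. A risk called minimal or highly unlikely is still a known risk. The sentences therefore conflict.

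**Step 2: what does *study procedure* mean?** There is no formal definition, so usage has to decide.
- Section 7.7 counts follow-up from discharge after it.
- Sections 7.4 and 7.5 describe it as the operation, with intra-operative data on its own CRF and scheduling relative to the baseline assessment.
- The opening sentence of Section 12.1 names study assessments and the study procedure as two separate things.

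MRI appears as an assessment in Table 7-1 and Section 7.7. On this usage it is not part of the study procedure.

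**Step 3: follow a minor MRI burn through the rules.**
1. Section 8.1 counts any undesirable clinical occurrence as an AE, so it qualifies.
2. It is non-serious under Section 8.2, so a relatedness filter applies.
3. Section 4.4.1 item 3, footnote 5 and Section 8.4 each admit it only if related to the device or the procedure. It is caused by neither.
4. Other forms do not catch it. The Malfunction CRF (Section 9) covers the sponsor's own system. The unscheduled-visit CRF (Section 7.8) covers ongoing shoulder-related issues.

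**Step 4: follow a serious MRI harm.** If it occurs after enrollment it is reported as an SAE regardless of cause. The gap is confined to non-serious events.

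**Step 5: count the scans.** Inputs are 3 follow-up MRIs per subject (Table 7-1, Section 7.7) and at most 150 subjects (Section 4.1).
- Within the AE reporting window: 3 × 150 = 450 scans at most.
- With baseline: 4 × 150 = 600 scans at most.

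The relevant ceiling is 450. Sections 7 and 8 start AE reporting at intra-operative enrollment, so the baseline scan precedes the window, and it may be ordinary pre-operative work-up. Attrition would lower the count.

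**The case against.** The strongest case on the other side has four parts.

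- **The MRI risks are disclosed.** Section 12.1 promises to inform patients about the complications of study assessments and then names each MRI risk. Read generously, the denial refers only to treatment with the same marketed device. This stands in part: nothing is concealed. But the sentence speaks of participating in the study, and participation includes the scans.
- **The word *procedure* is loose.** Sections 4.4.1 and 8.4 say procedure-related without the word *study*, Section 12.1 calls MRI a procedure, and inclusion criterion 7 speaks broadly of study-related procedures. An investigator could enter an MRI harm as procedure-related. This also stands in part. A reader might infer that no non-serious MRI harm could ever be reported, but without a formal definition the documents support only the absence of a clear category. Footnote 5 and the CRF items still point to surgery.
- **Limiting non-serious AEs is a legitimate choice** in a post-market study of cleared devices. That is so, and the rule is stated consistently. The weakness is only that the two categories do not cover the study's own assessments.
- **Post-operative MRI might be routine outside the study.** The documents do not settle this. If it is routine, Section 12.1 should say so.

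Two further inferences go too far. A reader might conclude that MRI harms cannot appear in the safety results at all, but serious ones after enrollment do. A reader might also conclude that subjects sign a misleading consent form, but the consent wording is not in the documents reviewed. Section 14.4 says only that the sponsor supplies a template.

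**Conclusion.** The point holds as a minor one. The denial of added risk in Section 12.1 contradicts the MRI risks listed in the same section. A non-serious harm from any of up to 450 follow-up study MRIs has no clear recording category.

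This rests on two assumptions: that the follow-up scans are not already routine care, since no section says they are, and that *study procedure* means the surgery, as usage indicates. The number of events missed cannot be estimated from the documents. By the protocol's own account it should be low. The primary tendon-thickness test, the sample size, the error rates and the efficacy outcomes are untouched.

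**What to change.** 1. In Section 12.1, replace the denial with a sentence such as: *The known incremental risks of participation are those of the study-required MRIs listed below.* Bring the next sentence, which equates the risks with those of treatment outside the study, into line.
2. Add *related to a study-required assessment* as a third relatedness category in Section 4.4.1 (item 3 and the sentence on how events are summarised), Table 7-1 footnote 5, Section 8.4 and the Adverse Event CRF. Summarise that category separately.
3. Check whether the consent template repeats the Section 12.1 sentence, and correct it only if it does.

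The cost is small edits to a few protocol passages and one extra CRF option. If the consent form has to change, Section 14.6 requires approval from everyone who approved the original protocol and from the IRB/EC before implementation, so notification alone would not be enough.

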12.2 BENEFITS

Participation in this study is voluntary. Subjects can obtain the same treatment without participating in this study. However, information gathered from this study will help the Sponsor to continue to evaluate long-term performance of the device when used alone or in conjunction with surgical repair to treat partial or full-thickness tears of the supraspinatus tendon.

13 DATA MANAGEMENT

13.1 DATA COLLECTION

Case report forms (CRFs) will be completed by the Investigator (or authorized study personnel) for each subject enrolled in the study. Data queries and edit checks will be used to reconcile discrepancies between data on the source documents and data entered on the CRFs. The Investigator must assure the accuracy and completeness of the recorded data. For the purpose of this study, the ASES and Constant shoulder surveys, as well as the Recovery/Satisfaction form, may act as their own source data.

13.2 DATA PROCESSING

All study documentation will be entered and maintained in a central database by the Sponsor or Sponsor-authorized representatives. Automatic and/or manual edit checks will be issued as necessary to correct discrepant data. Appropriate quality control measures will be established to ensure accurate and complete transfer of information from the study documentation to the central database. Data files will be exported from the central database for statistical analyses.

14 ADMINISTRATIVE RESPONSIBILITIES

The proposed study will be performed in accordance with all requirements set forth in the all applicable U.S. regulations, 21 Code of Federal Regulations (CFR) Parts 50 and 56, the World Medical Association Declaration of Helsinki, ISO 14155 (1) and (2), and any other applicable local laws and regulations.

14.1 SITE AND INVESTIGATOR SELECTION

Each site and Investigator selected to participate will be evaluated to ensure each has the capacity, volume of surgical candidates, and capability to comply with all informed consent and protocol requirements. In addition, surgeon experience performing mini-open and arthroscopic surgeries to treat rotator cuff tears will be evaluated. Each study site and Investigator are required to comply with applicable local legal and regulatory requirements and applicable U.S. federal regulations.

14.2 TRAINING

All Investigators (Principal, co-Investigator, sub-Investigator) must be Board Certified orthopaedic surgeons with experience performing mini-open or arthroscopic rotator cuff repairs. Prior to first enrollment, each participating surgeon will complete Sponsor-provided training on the Rotation Medical Rotator Cuff System.

The Sponsor will also be responsible for ensuring each site and Investigator are properly trained on the study protocol and applicable regulatory requirements.

To insure uniform data collection and protocol compliance, the Sponsor or Sponsorauthorized representatives will train the Study Coordinator(s) and study staff on all components of the study including the study protocol, techniques for the identification of eligible subjects, instructions for data collection during the procedure, and schedules for follow-up.

14.3 INSTITUTIONAL REVIEW BOARD (IRB) / ETHICS COMMITTEE (EC)

It is the Investigator's responsibility to obtain and maintain written approval of the final study protocol and Informed Consent from the appropriate IRB or Ethics Committee. Investigators are responsible for submitting and obtaining initial and continuing review of the trial by their IRB/EC. It is also the Investigator's responsibility to notify the IRB/EC of any amendments to these documents. A copy of the written approval must be forwarded to the Sponsor prior to first device shipment. The written approval must identify the study and document the date of review.

The Investigators must keep on file all study-related correspondence with the IRB/EC and forward copies of such correspondence to the Sponsor.

14.4 INFORMED CONSENT FORM (ICF)

Informed consent must be obtained in accordance with the applicable guidelines on 21 CFR Part 50, current GCP, the Declaration of Helsinki, ISO 14155 (1) and (2), or local regulations and laws, whichever represents the greater protection of the individual. The subjects must be informed about their right to withdraw from the study at any time and for any reason without sanction, penalty, or loss of benefits to which the subject is otherwise entitled and also informed that withdrawal from the study will not jeopardize

their future medical care. The institutional standard subject consent form does not replace the study informed consent form (ICF).

The Sponsor will provide a study-specific template ICF to each site for IRB/EC submission. This template may be modified to suit the requirements of the individual study site. The Sponsor must pre-approve all changes to the ICF prior to initial submission to the IRB/EC. The Informed Consent Form must be approved by the IRB/EC prior to device shipment and a copy must be retained at the investigational site along with the other investigational forms. A signed copy of the consent form must be given to each subject enrolled in the study and a signed copy of the consent form must be retained for each subject at the investigational site.

Modifications to the study-specific Informed Consent Form and/or any written information distributed to subjects must be approved by the Sponsor, and the IRB/EC as necessary.

